### **10.4 Prior and Concomitant Medications**

Prior medications are those medications that were stopped prior to investigational product administration. Concomitant medications are medications that are taken at least once after investigational product administration. Medications stopping on the same day as investigational product administration will be considered as concomitant medications.

All prior and concomitant medications will be listed. In addition, for each treatment group, the number and percentage of subjects taking at least one concomitant medication will be presented.

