5.7. PHARMACOKINETIC ANALYSIS SET [PK]

The PK analysis set (PKAS) will contain all subjects in the SAF set who received LYR-210 and have at least one evaluable plasma drug concentration data point post-Day 1 available. As concentration data are required to assign the PK analysis set, this can only be done at study unblinding, at the time of the primary analysis. Subjects will be analyzed according to the actual treatment successfully received.

Subjects who have used any Mometasone Furoate drugs within one day prior to a PK blood draw would be

identified by “MOMETASONE” in the Base Name of concomitant medications. These PK blood draw timepoints will be excluded from analysis. Similarly, results from PK blood draw timepoints after subjects reported any depot dislodgement will also not be analyzed.

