12. MEDICATIONS

Medications other than CS medical treatment history (see Section 10) will be coded World Health Organization Drug Dictionary (WHO-DD) version March 2020 or later. No Anatomical Therapeutic Class (ATC) coding will be performed for this study.

See APPENDIX 2 for handling of partial dates for medications. In the case where it is not possible to define a medication as prior, concomitant, or post-treatment, the medication will be classified by the worst case; i.e. concomitant.

- ‘Prior’ medications are medications which started and stopped prior to the bilateral insertion/Sham procedure or treatment attempt.
- ‘Concomitant’ medications are medications which:
 - started prior to the bilateral insertion/Sham procedure/treatment attempt AND were ongoing or ended after the bilateral insertion/Sham procedure/treatment attempt;
 - started on the day of the bilateral insertion/Sham procedure/treatment attempt;
 - started after the bilateral insertion/Sham procedure/treatment attempt but before or on the removal/Sham removal + 28 days.
- ‘Post-treatment’ medications are medications which started after the bilateral removal/Sham procedure + 28 days.

Prior, Concomitant and Post Medications will be listed by WHO drug name concatenated with base name for the SAF analysis set.

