APPENDIX 2. PARTIAL DATE CONVENTIONS

ALGORITHM FOR TREATMENT EMERGENCE OF ADVERSE EVENTS

Start Date	Stop Date	Action
Known	Known/Partial/ Missing	If start date < insertion procedure, then Prior If insertion procedure <= start date <= removal procedure + 28 days , then TEAE If start date > removal procedure + 28 days, then Post-Treatment AE
Partial, but known components show that AE started before insertion procedure	Known/Partial/ Missing	Assumed Prior
Partial, known components show that AE started on/after insertion procedure but before/on removal procedure + 28 days OR Missing	Known/Partial/ Missing	Assumed TEAE
Partial, known components show that AE started after removal procedure + 28 days	Known/Partial/ Missing	Assumed Post-Treatment AE

ALGORITHM FOR PRIOR/CONCOMITANT MEDICATIONS

Start Date	Stop Date	Action
Known	Known	If stop date < insertion procedure, assign as Prior If stop date >= insertion procedure and start date <= removal procedure+28 days, assign as Concomitant If start date > removal procedure+28 days, assign as Post-Treatment.

Start Date	Stop Date	Action
	Partial	If known date parts of stop date < insertion procedure, assign as Prior If known date parts of stop date >= insertion procedure and start date <= removal procedure+28 days, assign as Concomitant If start date > removal procedure+28 days, assign as Post-Treatment
	Missing	If stop date is missing could never be assumed a Prior medication If start date <= removal procedure+28 days, assign as Concomitant If start date > removal procedure+28 days, assign as Post-Treatment
Partial	Known	If stop date < insertion procedure, assign as Prior If stop date >= insertion procedure and known date parts of start date <= removal procedure+28 days, assign as Concomitant If known date parts of start date > removal procedure+28 days, assign as Post-Treatment
	Partial	If known date parts of stop date < insertion procedure, assign as Prior If known date parts of stop date >= insertion procedure and known date parts start date <= removal procedure+28 days assign as Concomitant If known date parts of start date > removal procedure+28 days, assign as Post-Treatment
	Missing	If stop date is missing could never be assumed a Prior medication If known date parts of start date <= removal procedure+28 days, assign as Concomitant If known date parts of start date > removal procedure+28 days, assign as Post-Treatment

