Missing	Known	If stop date < insertion procedure, assign as Prior If stop date >= insertion procedure, assign as Concomitant Cannot be assigned as Post-Treatment
	Partial	If known date parts of stop date < removal procedure+28 days, assign as Prior If known date parts of stop date >= removal procedure+28 days, assign as Concomitant Cannot be assigned as 'Post-Treatment'
	Missing	Assign as Concomitant

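### SAP Appendix 2 uses removal + 28 days instead of insertion as the Prior cutoff for medications with a missing start and partial stop date, so some on-treatment drugs are labelled Prior

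*SAP*

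**What the plan says.** SAP Section 12 defines prior "medications are medications which started and stopped prior to the bilateral insertion/Sham procedure or treatment attempt". When a medication cannot be classed, the same section gives the default: "the medication will be classified by the worst case; i.e. concomitant". Protocol Section 10.4 likewise ties Prior to stopping before product administration, and counts a drug stopped on the administration day as concomitant.

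SAP Appendix 2 turns this into a table of start-date and stop-date patterns. For a known or partial start with a partial stop, the Prior rule is "If known date parts of stop date < insertion procedure, assign as Prior". For a missing start with a known stop, the Concomitant rule is "If stop date >= insertion procedure, assign as Concomitant". For a missing start with a partial stop, the two rules are "If known date parts of stop date < removal procedure+28 days, assign as Prior" and "If known date parts of stop date >= removal procedure+28 days, assign as Concomitant".

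The classes are used in three places:

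- SAP Section 12 lists prior, concomitant and post-treatment medications for the safety set.
- Protocol Section 10.4 says that, by treatment group, "the number and percentage of subjects taking at least one concomitant medication will be presented".
- SAP Section 5.7 concerns mometasone used within one day before a PK draw. It identifies that use by the drug's name "in the Base Name of concomitant medications. These PK blood draw timepoints will be excluded from analysis".

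**The concern.** One row of a nine-row table has a different time anchor from the rest, and the difference runs against the SAP's own default. Where the class is uncertain, Section 12 sends the drug to Concomitant. This row sends it to Prior, even when the known stop month proves that the drug was taken after insertion.

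A program written literally from Appendix 2 would place drugs taken during treatment under Prior in the listings and omit them from any concomitant count. On-study mometasone is foreseeable, because Protocol Section 6.4.4 allows intranasal mometasone spray as rescue after Week 4 and PK samples follow at Weeks 12, 24 and 28. The class may therefore also bear on which PK values are kept.

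**Working it through.** The plan states no figure that depends on this rule, so the check is a comparison of rows followed by a worked example.

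**Step 1: the rows of Appendix 2**

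| Start date | Stop date | Cutoff for Prior |
|---|---|---|
| Known | Known | insertion |
| Known | Partial | insertion |
| Known | Missing | Prior not possible |
| Partial | Known | insertion |
| Partial | Partial | insertion |
| Partial | Missing | Prior not possible |
| Missing | Known | insertion |
| Missing | Partial | **removal + 28 days** |
| Missing | Missing | always Concomitant |

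Six rows can return Prior. Five use insertion and one does not. SAP Section 3.3, which lists changes from the protocol, does not mention the exception.

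**Step 2: width of the affected window**

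The treatment stage is 24 weeks (Protocol Section 4.1.2), with Week 24 at target Day 169 (SAP Table 1). With removal on that day, the cutoff is 24 × 7 + 28 = 196 days after insertion, which is Day 197. Early removal shortens the window.

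**Step 3: one record under different levels of date detail**

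Assumed dates: insertion 15 January 2020, removal 1 July 2020 (Day 169), removal + 28 days = 29 July 2020 (Day 197). The start is missing and the true stop is in April 2020.

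- Complete stop date: April is after insertion, so **Concomitant**.
- Month and year only: April 2020 is before July 2020, so **Prior**.
- Stop date missing: **Concomitant**.

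Knowing the month, which proves on-treatment use, moves the drug out of the on-treatment class.

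**Step 4: how many stop months change class**

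With the same dates and month-level stops:

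| Stop month | As written | With insertion cutoff |
|---|---|---|
| December 2019 | Prior | Prior |
| January 2020 | Prior | Concomitant |
| February to June 2020 | Prior | Concomitant |
| July 2020 and later | Concomitant | Concomitant |

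Six months change. February to June, five months, lie wholly after the insertion month. For January the month alone does not settle it, and the Section 12 default would give Concomitant.

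Repeating this over 366 consecutive assumed insertion dates, with removal always on Day 169, gives 6 changed months for 210 dates (5 of them certain) and 7 for the other 156 (6 certain).

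**Step 5: where the label can reach**

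- Listings: directly.
- Protocol count of subjects with at least one concomitant medication: only if the mislabelled drug is the subject's sole concomitant medication.
- PK exclusion (SAP Section 5.7): only if the search runs on the derived class.
- Per-protocol set: not affected. SAP Section 5.6 takes the prohibited-medication exclusions from medical data review and the deviation log.
- Week 4 and Week 24 symptom scores, MRI response and time to treatment failure: not affected. They come from the diary, the imaging data and, for physician recommendations, the Follow-up eCRF (SAP Sections 15.1.1 and 15.2.1).

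**The case against.** The strongest reply is that this is a drafting slip with little reach, and much of that stands.

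- **PK.** A reader might infer that mislabelled mometasone records escape the exclusion and leave contaminated plasma values in the PK summary. The documents do not support that as stated. Section 5.7 does not say whether its concomitant medications are the Appendix 2 class or the collected records, and the protocol's schedule of assessments uses the same term for the data collected. On the second reading the Prior label has no effect. On either reading, a record with no start date and only a month or year for its stop cannot be placed within one day of a draw, and the SAP gives no imputation rule for it. Correcting the cutoff would not by itself exclude any draw.
- **Likelihood.** Rescue mometasone is started on the investigator's decision, so its start should be known. Protocol Section 11.8 requires missing data to be queried before lock. A rescue spray with no start date is improbable, though not excluded.
- **The count.** All subjects receive topical anesthetic and decongestant on Day 1 (Protocol Section 6.2.1). SAP Section 12 makes drugs started that day concomitant. If they are recorded as Protocol Section 6.4 requires, the percentage is about 100% in every arm whatever this row does. SAP Section 12 itself plans listings only.

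None of this defends the cutoff. It limits the consequence and shows that Section 5.7 has a separate gap on incomplete dates.

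**Conclusion.** Wrong as written, and minor. The removal + 28 days cutoff conflicts with the five other rows that can give Prior, with the SAP definition and default, and with the protocol. It labels drugs certainly taken during treatment as Prior.

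The window is nominally 196 days per subject, but that measures the width of the rule and is not an effect on any estimate. The month counts rest on scheduled removal, month-level stop dates and assumed calendar dates. How many medications have this date pattern is not given in the documents and is probably small.

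The certain consequence is mislabelling in the listings and in any concomitant-use tabulation. An effect on the PK exclusion is possible but conditional. No primary or key secondary efficacy result changes.

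**What to change.** In the missing-start, partial-stop row of Appendix 2, replace the removal + 28 days cutoff with the insertion procedure in both lines. Known stop parts before insertion then give Prior, and known stop parts on or after insertion give Concomitant. This matches the missing-start, known-stop row directly above and leaves the statement that the row cannot yield Post-Treatment as it is.

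In Section 5.7, state that the mometasone search covers all recorded medications whatever their class, and add a rule for records whose dates are too incomplete to place relative to a draw. This is needed because the cutoff correction alone does not trigger the one-day exclusion.

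The cost is a short edit to one row, one or two sentences in Section 5.7, and the matching program changes. No downside to the cutoff correction was identified.
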